#### 6.6 Efficacy Assessments

#### 6.6.1 Imaging Assessment for the Study

All the patients who enrolled into study will undergo efficacy assessments for overall response rate, disease control rate, progression free survival and overall survival, as defined in Section 8.5. A baseline imaging study preferably CT scan of chest/abdomen/pelvis with IV contrast (permitting no contraindication to contrast) will be performed followed by every nine weeks interval while the patient is on study. Efficacy end points will be assessed according to RECIST 1.1 criteria.

#### 6.6.2 Definitions of Measurable and Non-Measurable Disease

#### 6.6.2.1 Measurable Disease

Tumor lesions: Must be accurately measured in at least one dimension (longest diameter in the plane of measurement is to be recorded) with a minimum size of 10 mm by CT scan (CT scan slice thickness no greater than 5 mm).

Malignant lymph nodes: To be considered pathologically enlarged and measurable, a lymph node must be 15 mm in short axis when assessed by CT scan (CT scan slice thickness recommended to be no greater than 5 mm). At baseline and in follow-up, only the short axis will be measured and followed.

#### 6.6.2.2 Non-Measurable Disease

All other lesions, including small lesions (longest diameter <10 mm or pathological lymph nodes with 10 to <15 mm short axis) as well as truly non-measurable lesions. Lesions considered truly non-measurable include: leptomeningeal disease, ascites, pleural or pericardial effusion, inflammatory breast disease, lymphangitic involvement of skin or lung, abdominal masses/abdominal organomegaly identified by physical exam that is not measurable by reproducible imaging techniques.

#### 6.6.3 Response Criteria

All patients will undergo re-evaluation imaging scans every nine weeks from the start of treatment as per the study schedule to determine response to treatment. Following designations will be assigned according to iRECIST. (see appendix below for differences in RECIST 1.1 and iRECIST),

#### 6.6.3.1 Complete Response (iCR)\*

Defined as disappearance of all target lesions. Any pathological lymph nodes (whether target or non-target) must have reduction in short axis to <10 mm.

#### 6.6.3.2 Partial Response (iPR)\*

At least a 30% decrease in the sum of diameters of target lesions, taking as reference the baseline sum diameters.

# 6.6.3.3 Progressive Disease (PD)\*

At least a 20% increase in the sum of diameters of target lesions, taking as reference the smallest sum on study (this includes the baseline sum if that is the smallest on study). In addition to the relative increase of 20%, the sum must also demonstrate an absolute increase of at least 5 mm.

Unconfirmed PD (iUPD) requires confirmation, which is done on the basis of observing either a further increase in size (or in the number of new lesions) in the lesion category in which progression was first identified in (ie, target or non-target disease), or progression (defined by RECIST 1.1) in lesion categories that had not previously met RECIST 1.1 progression criteria. However, if progression is not confirmed, but instead tumor shrinkage occurs (compared with baseline), which meets the criteria of iCR, iPR, or iSD, then the bar is reset so that iUPD needs to occur again (compared with nadir values) and then be confirmed (by further growth) at the next assessment for confirmed progressive disease (iCPD) to be assigned. If no change in tumor size or extent from iUPD occurs, then the timepoint response would again be iUPD.

## 6.6.3.4 Stable Disease (iSD)\*

Neither sufficient shrinkage to qualify for PR nor sufficient increase to qualify for PD, taking as reference the smallest sum diameters while on study.

\* May have had unconfirmed progressive disease (iUPD) (1 or more instances), but not confirmed progressive disease (iCPD), prior to complete response (iCR), partial response (iPR) or stable disease (iSD). "i" indicates immune responses assigned using iRECIST.

## 6.6.4 Tumor Determination of Stage by Tumor, Lymph Nodes, Metastasis (TNM) Classification

In some circumstances, it may be difficult to distinguish residual disease from normal tissue. When the evaluation of CR depends on this determination, it is recommended that the residual lesion be investigated (fine needle aspirate/biopsy) before confirming the complete response status.

#### 6.7 Biopsies and Immune Monitoring

All patients undergoing treatment with OBP-301 will have tissue biopsies along with correlative blood samples. Tissue biopsies will be performed with every injection of OBP-301. Correlative blood samples will be taken before the start of study treatment, during treatment and post-treatment as described in the section of study schedule. Blood and biopsy samples will be retained for future research if informed consent has been obtained from the patient.

# 7 ADVERSE EVENTS

# 7.1 Definitions

# 7.1.1 Definition of an Adverse Event

An AE is any event, side effect, or other untoward medical occurrence that occurs in conjunction with the use of a medicinal product in humans, whether or not considered to have

a causal relationship to this treatment. An AE can, therefore, be any unfavorable and unintended sign (that could include a clinically significant abnormal laboratory finding), symptom, or disease temporally associated with the use of a medicinal product, whether or not considered related to the medicinal product.

Events meeting the definition of an AE include:

- Exacerbation of a chronic or intermittent pre-existing condition including either an increase in frequency and/or intensity of the condition.
- New conditions detected or diagnosed after IP administration even though it may have been present before the start of the study.
- Signs, symptoms, or the clinical sequelae of a suspected interaction.
- Signs, symptoms, or the clinical sequelae of a suspected overdose of either IP or a concomitant medication (overdose per se will not be reported as an AE/SAE).

"Lack of efficacy" or "failure of expected pharmacological action" per se will not be reported as an AE or SAE. However, the signs and symptoms and/or clinical sequelae resulting from lack of efficacy will be reported if they fulfil the definition of an AE or SAE.

Events that do not meet the definition of an AE include:

- Medical or surgical procedure (e.g., appendectomy). The condition that leads to the procedure is an AE.
- Situations where an untoward medical occurrence did not occur (e.g., social and/or convenience admission to a hospital).
- Anticipated day-to-day fluctuations of pre-existing disease(s) or condition(s) present or detected at the start of the study that do not worsen.

If there is evidence of an AE through report or observation, the Investigator or designee will evaluate further and record the following information:

- Date of onset and resolution
- Classification of 'serious' or 'non-serious'
- Severity
- Causality/relation to study treatment
- Action taken regarding IP (no action taken, study treatment interrupted, study treatment discontinued)
- Medication or additional treatment (no medication additional treatment, concomitant medication, non-drug therapy, other)
- Outcome /Status (recovered, recovered with sequelae, recovering, ongoing, fatal unknown)

# 7.1.2 Severity of an Adverse Event

The intensity of AEs/SAEs will be graded according to the National Cancer Institute Common Terminology Criteria for Adverse Events (NCI-CTCAE) version 4.03 (dated 14 June 2010).

Should an event be missing in the NCI-CTCAE, the following 5-point scale is to be used:

- Mild: Discomfort noticed, but no disruption of normal daily activity
- Moderate: Discomfort sufficient to affect normal daily activity

- Severe: Inability to work or perform normal daily activity
- Life-threatening: Risk of death at the time of the event
- Fatal: The patient died

The correspondence between the 2 scales is as follows:

NCI-CTCAE	5 point scale
1	Mild
2	Moderate
3	Severe
4	Life-threatening
5	Fatal/Death

NCI-CTCAE = National Cancer Institute Common Terminology Criteria for Adverse Events

# 7.1.3 Causal Relationship of an Adverse Event

Causal relationship of an adverse event to the IP will be assessed by the Investigator as follows:

Not related:	The event is clearly related to other factors such as the participant's clinical state, therapeutic interventions or concomitant drugs administered to the participant. This is especially so when an event occurs before the commencement of treatment with the IPs.				
Unlikely:	The experience was most likely produced by other factors such as the participant's clinical state, therapeutic interventions or a concomitant drug administered to the participant and does not follow a known response to the trial IP.				
Possible:	The experience follows a reasonable temporal sequence from the time of IP administration and/or follows a known response to the trial IP, but could have been produced by other factors such as the participant's clinical state or other therapeutic interventions or concomitant drugs administered to the participant.				
Probable:	The experience follows a reasonable temporal sequence from the time of IP administration and follows a known response to the trial IP, and cannot be reasonably explained by other factors such as the participant's clinical state or other therapeutic interventions, or concomitant drugs administered to the participant.				
Definite:	The experience follows a reasonable temporal sequence from the time of IP administration and follows a known response to the trial IP, and cannot be reasonably explained by other factors such as the participant's clinical state or other therapeutic interventions or concomitant drugs administered to the patient and in addition one or more of the following:				
	
 
Occurs immediately following trial IP administration
 
Improves on stopping the trial IP
 
				

• Reappears on repeat exposure

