Investigational Product Administration:	OBP-301, the investigational product (IP) is formulated in 20 mM Tris pH 8.0, 25 mM NaCl with 2.5% glycerin, USP by volume. OBP-301 will be injected into the target tumor lesions.
Planned Patients:	41 patients in total for both stage 1 and 2, to achieve 37 evaluable patients.
Participant Selection	Inclusion Criteria:
Criteria:	Patients who meet all of the following criteria will be considered for inclusion in the study:
	
 
Be willing and able to provide written informed consent for the trial.
 
Be ≥18 years of age on the day of signing the informed consent.
 
Have an Eastern Cooperative Oncology Group (ECOG) performance status of 0-2.
 
Have histologically or cytologically confirmed advanced or metastatic gastroesophageal adenocarcinoma, at least 1 cm in size and amenable to intratumoral injection.
 
Patient must have received at least 2 line of systemic therapy for advanced disease.
 
Tumor must be PD-L1 positive, as defined by a combined positive score (CPS).
 
Have one or more measurable lesions based on iRECIST.
 
Be willing to provide tissue; newly obtained biopsy specimens or formalin-fixed, paraffin-embedded (FFPE) block specimens.
 
Female subjects of childbearing potential have a negative urine or serum pregnancy test within 7 days prior to enrollment. If the urine test is positive or cannot be confirmed as negative, a serum
 

10.	pregnancy test will be required. If a serum pregnancy test is required it can be performed on the same day as the urine pregnancy test. The serum pregnancy test must also be completed 7 days prior to enrollment. And male / female subjects of childbearing potential must agree to use an adequate method of contraception starting with signing the informed consent through 120 days after the last dose of study medication. Demonstrated adequate organ function as defined in following criteria. All screening labs should be performed within 14 days of enrollment. Note: Subject must not have taken transfusion, hematopoietic agent; granulocyte-colony stimulating factor (G- CSF) etc., and/or oxygen supplementation within 7 days before the screening labs.

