# 7.2.3 Follow-up of Adverse Events and Serious Adverse Events

In this study, non-serious AEs will be reported in all participants from Treatmet 1. Non-serious AEs reported from the time of consent to injecting on Day 1 will be recorded as medical history. Serious adverse events (SAEs) will be reported in all patients (enrolled and not enrolled) from the time of consent. Study procedure-related AEs will be evaluated specifically from the time of consent until the administration of OBP-301. Treatment-emergent AEs will be evaluated from the time of injecting with IP until the Final Visit. The Investigator is responsible to ensure that follow-up includes any supplemental investigations as may be indicated to elucidate as completely as practical the nature and/or causality of the AE/SAE. This may include additional laboratory tests or investigations, histopathological examinations, or consultation with other health care professionals.

All non-serious AEs that are ongoing at the Final Visit will be marked as ongoing on the AE eCRF page in the REDCap database.

All SAEs that are ongoing at the Final Visit must be followed until resolution, until the condition stabilizes, until the event is, in the opinion of the Investigator, stabilized or determined to be chronic, or until the participant dies or is lost to follow-up. SAEs that occur after the Final Visit, that are thought to be related to the administration of OBP-301, should be reported to Oncolys BioPharma Inc. or designee.

If a participant is withdrawn because of an AE, the Investigator must arrange for the participant to have appropriate follow-up care until the AE is resolved or has stabilized. Unresolved AEs will be followed until the last scheduled follow-up visit or until the Investigator and Medical Monitor determine that further follow-up is no longer indicated. Oncolys BioPharma Inc. may request that the Investigator perform or arrange for the conduct of supplemental measurements and/or evaluations. If a participant dies during participation in the study or during a recognized Follow-up Period, Oncolys BioPharma Inc. should be provided with a copy of any post-mortem findings, including histopathology.

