#### 8.7 Safety Analyses

# 8.7.1 Safety Endpoints

The primary safety endpoint is to examine the safety of multiple OBP-301 intratumoral injections in combination with pembrolizumab in advanced esophagogastric cancer.

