#### 8.7.2 Summary of Adverse Events

All adverse events, as defined in Section 7, will be recorded for each patient. Adverse events will be tabulated for all patients by: first occurrence of each adverse event, maximum severity, and relationship to treatment. Treatment-related AEs and serious AEs will be tabulated separately, by first occurrence, maximum severity, and strongest relationship to treatment. A listing of all AEs will also be included, per patient, including onset/resolution date, severity, relationship to study treatment, and action regarding IP. A listing of all discontinuations, injection delays, and deaths due to adverse events in the study will be included.

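### Causality is defined only against OBP-301 and 'treatment-related' is undefined for the combination, so the treatment-related AE tables cannot reliably show combination, pembrolizumab or procedure toxicity

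*Combined protocol and SAP*

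**What the plan says.** - **The IP.** The synopsis equates the IP with the virus: "OBP-301, the investigational product (IP) is formulated in 20 mM Tris pH 8.0". Section 5.1 does the same, and 5.2.1 has pembrolizumab coming from commercial suppliers.
- **Causality.** Section 7.1.3 opens: "Causal relationship of an adverse event to the IP will be assessed by the Investigator as follows". Its lowest category reads: "The event is clearly related to other factors such as the participant's clinical state, therapeutic interventions or concomitant drugs administered to the participant". *Unlikely* needs another most likely cause and an event that also fits this condition: "and does not follow a known response to the trial IP". *Possible* keeps an event with a plausible time course or a known IP response, even if another drug could explain it.
- **Action taken.** Section 7.1.1 lists "Action taken regarding IP (no action taken, study treatment interrupted, study treatment discontinued". The AE listing in 8.7.2 likewise covers only action on the IP.
- **Procedures.** Section 7.2.3 states: "Study procedure-related AEs will be evaluated specifically from the time of consent until the administration of OBP-301". The Schedule of Events (6.1) puts injections with biopsies on Days 1, 15, 29 and 43.
- **Safety aim.** Section 8.7.1: "The primary safety endpoint is to examine the safety of multiple OBP-301 intratumoral injections in combination with pembrolizumab". Section 2.1 lists the same aim as a primary objective.
- **Tables.** Section 8.7.2: "Treatment-related AEs and serious AEs will be tabulated separately, by first occurrence, maximum severity, and strongest relationship to treatment". It defines neither 'treatment' nor the causality level that counts as related.

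**The concern.** The safety question is about two agents and a repeated invasive procedure, but causality is assessed for one agent. The treatment-related table is the usual attributed summary of toxicity. If it reflects the virus alone, it understates what the regimen did. If events near an injection default to *Possible*, it also charges the virus with events that belong to the antibody or the endoscopy.

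The protocol relies on the attributions it does not ask sites to record. Supportive care in 5.2.6 depends on the investigator judging an event related to pembrolizumab. A discontinuation criterion in 6.1.4 turns on toxicity from OBP-301 or the endoscopic procedure. With three sites and no defined term, the same event could be scored differently. Attribution made at the time of the event is hard to reconstruct at database lock.

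**Working it through.** The plan states no figure on this point, so there is none to reproduce. The check sets the sections against each other and then bounds the size.

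**1. Where three kinds of event land under 7.1.3**

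| Event | Literal score against OBP-301 | Treatment-related table, if fed by 7.1.3 |
|---|---|---|
| Clearly due to pembrolizumab, e.g. late colitis on antibody alone | *Not related* | absent |
| Clearly due to a Day 15, 29 or 43 endoscopy or biopsy | *Not related* | absent |
| Ambiguous, soon after an injection | *Possible* | present, charged to OBP-301 |

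The last column assumes that 'related' means *Possible* or stronger. That is the threshold used in 8.7.9; 8.7.2 gives none.

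**2. How often ambiguity arises.** Pembrolizumab is scheduled on Days 4, 25 and 46. The gaps since the latest injection are 4 − 1 = 3, 25 − 15 = 10 and 46 − 43 = 3 days. Section 1.2 lists transaminitis and pneumonia among expected OBP-301 effects, which overlap with the hepatic and lung toxicities in Table 2 of 5.2.4. During the injection period, *Possible* is often available. Events clearly due to the antibody are easier to identify once injections have ended.

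**3. The procedure window.** Taking 'administration' in 7.2.3 as the first dose, 3 of the 4 scheduled injection and biopsy visits, and any fifth injection, fall after specific procedure evaluation ends. Treatment-emergent AEs are still collected to the Final Visit. What is lost is the procedure label.

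**4. What 'treatment' means.** Section 7.1.1 records relation to study treatment, and its action-taken item uses that term for the IP. Table 2 in 5.2.4 uses it for pembrolizumab. The term is not fixed, and 7.1.3 is the only scale available to populate 8.7.2.

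**5. Size.** The documents give no AE rates for the combination, so the rates below are assumptions.

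Patients missing from the table = N × r × f, where N = 41 (planned enrolment), r is the share with a pembrolizumab-attributed Grade 3 or worse event, and f is the share of those scored below *Possible*.
- r = 0.10, f = 1: 41 × 0.10 = 4.1
- r = 0.20, f = 1: 41 × 0.20 = 8.2
- f = 0.5: 2.05 and 4.1

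With f = 1 the result is an upper bound for these rates.

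A second illustration counts events related to either agent. If 30% of 41 patients (12) have one, the rate is 12/41 = 29% (exact 95% CI 16.1% to 45.5%). If half of those patients had events clearly due to pembrolizumab only, an OBP-301-only table shows 6/41 = 15% (5.6% to 29.2%). With totals of 20% to 40% and pembrolizumab-only shares of 25% to 75%, the number missing runs from 8 − 6 = 2 to 16 − 4 = 12.

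**The case against.** A reader might infer that the tables leave out all pembrolizumab-caused events, or that the safety report could look clean while patients stop pembrolizumab for immune toxicity. The documents do not support either reading.

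- Because 'treatment' is undefined in 8.7.2 and 'study treatment' is used for both agents, omission follows from the literal reading of 7.1.3. It is not a stated rule.
- *Not related* requires a clear alternative cause. Overlapping events, or events close to an injection, can be scored *Possible* and enter the table.
- Section 8.7.2 tabulates and lists all AEs, and separately lists AE-related discontinuations, injection delays and deaths. The synopsis tabulates toxicities with exact intervals and no attribution filter. Section 7.2.5 requires SAE reports regardless of relation to the IP.
- The stopping rule in 8.7.9 counts Grade 3 or worse colitis, pneumonitis, nephritis and raised liver tests as immune-related without requiring attribution to OBP-301.
- Section 7.1.1 is a list of items to record, not the eCRF, so a pembrolizumab action field may exist. Section 8.1 also leaves full analysis detail to a SAP.
- In a single-arm trial where everyone gets both agents, attribution by component is investigator opinion and does not identify separate effects.

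All of this stands, and it limits the consequence to the attributed tables. It does not repair them. The all-AE outputs do not say which component was judged responsible, and a SAP can define a table but cannot supply a judgement that sites were not asked to make. Scores of *Possible* also feed the OBP-301 parts of 8.7.9, including the halt for a related death.

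**Conclusion.** The point holds in limited form. Causality is specified only for OBP-301, action taken only for the IP, and specific procedure attribution only before dosing, while 'treatment-related' is undefined for the combination. The treatment-related tables can err in both directions: clear antibody or procedure events drop out, and ambiguous ones are charged to the virus.

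The number affected cannot be known from the documents. The 4 to 8 of 41 is an upper bound under an assumed 10–20% rate with every such event scored below *Possible*; it is not a forecast. The defect itself depends on none of these assumptions.

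The response-rate decision and event capture are unaffected, and the immune-related part of the stopping rule does not depend on OBP-301 attribution. This is a cheap improvement that should be made, not a flaw that undermines the trial.

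**What to change.** - **7.1.3:** record causality separately for OBP-301, pembrolizumab and the injection/biopsy procedure, on the same five categories.
- **7.1.1:** record action taken for each drug, and carry both into the 8.7.2 listing.
- **7.2.3:** extend procedure attribution through all injection and biopsy visits to the Final Visit.
- **8.7.2:** define 'treatment-related' as at least possibly related to any of the three, and tabulate it overall and by component. Describe the component tables as investigator attribution.
- **8.7.9:** leave the attribution wording of the stopping rule unchanged.

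The cost is two or three extra fields per AE and a revised table shell. The downsides are slightly more site data entry and a higher reported treatment-related AE count. The change should be prospective, because attribution is hard to recover later.
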